10.2 Sample Size, Study Power, and Significance

A sample size of 954 is required to detect a difference of at least 4 points on the cognitive sub-score at 2 years corrected postnatal age.

This calculated sample size assumes 90 % power, 5 % significance level to detect a mean difference of 4 points in the primary outcome for a known population standard deviation of 15 points, with a 2-sided t-test, 10 % loss to follow-up, and 30 % adjustment for multiple births.

- A 2 sample t-test for mean difference of 4 points with SD of 15 points = 297 subjects/group resulting in a total unadjusted sample size of 594.
- The unadjusted sample size was rounded up to 600, then adjusted for expected 30 % prevalence of multiple births in the recruited population, and a 10 % loss to follow-up for the long-term outcome. 600/0.7/0.9 = 952.3 subjects
- The final sample size was rounded to 954, to ensure an even allocation of subjects to the two study groups.

A blinded interim analysis will be performed after 25 % and 50 % of participants have reached the 2 year endpoint to assess the assumptions in the sample size calculation.

Sample sizes for sub-studies target 80 % power to detect 0.5 SD mean difference with significance at the 5 % level.

Circadian rhythmicity will be assessed using cosinor analysis (non-linear regression) to determine mesor, amplitude, and acrophase of rhythms.

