- Infants and parents recruited to the sleep sub-study from KEMH or from Fiona Stanley Hospital (FSH), will also be invited to participate in physiological studies to measure how the cycled light and noise intervention influences sleep during hospitalisation (phase 1) and after discharge (phase 2).
 - Phase 1 (Completed December 2021): sleep and wakefulness will be measured using actigraphy at baseline, 7 d, 14 d, 28 d, and then every 4 weeks until 36 w postmenstrual age in infants recruited from KEMH.
 - Phase 2: sleep and wakefulness will be measured in both the infant and the main caregiver (parent) using actigraphy at 36 w postmenstrual age (or prior to discharge home, whichever comes first), at 2 months corrected postnatal age and at 6 months corrected postnatal age. Saliva swabs will also be obtained from the infants before they go to sleep at night, and again when they wake in the morning, at each of these times.

Key reported measures will include:

- Total sleep time
- Total day (6AM-8PM) and night (8PM-6AM) sleep
- Sleep/activity ratio
- Number of sleep awakenings after sleep onset
- Longest continuous sleep during daytime and night-time
- Peak salivary melatonin
- Day:night salivary melatonin ratio

5.1.7 Magnetic Resonance Imaging sub-study

MRI outcomes will include a calculation of a global abnormality score, derived from metrics obtained from T1- and T2-weighted images. Two different scoring systems will be applied to the conventional sequences.^{55,56}

Other MR measures of cerebral integrity will be derived from diffusion weighted imaging and include: Fractional anisotropy apparent diffusion coefficient in multiple areas of the brain.

An analysis of 208 MR images (n=104 from each group) will identify differences in the primary outcome of MRI Global Brain Abnormality Score (GBAS) of 2.85 assuming a standard deviation of 5 and adjusting for missing subjects (10 %) and 30 % multiple births.

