5.3 Minimisation of Bias

Infants meeting study eligibility criteria will be randomised to a control environment or a cycled environment (light and noise) from birth until discharge. Randomisation will use variable block sizes (block size 4 to 6) stratified by both gestation (<28 w, 28⁰-31⁶ w PMA) and study site, using the concealed randomisation facility built into the REDCap database via computer generated, randomisation tables developed and uploaded by the trial biostatistician ([name]) and maintained by the Trial Management Team at the Telethon Kids Institute. Randomisation will maintain equal group sizes between the two study arms. Infants from multiple pregnancies will be assigned to the same group, to ensure planned secondary analyses on parent mental well-being and attachment are not confounded by conflicting infant circadian rhythms.

Blinding of families, healthcare providers during initial hospitalisation, and the co-ordinating study investigators to group allocation is not possible for this intervention. However, outcome assessors and data analysts will be blinded to allocation.

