The primary sites currently include the King Edward Memorial Hospital (WA), Fiona Stanley Hospital (WA), Monash Newborn at Monash Children's Hospital (VIC), Women and Children's Hospital (SA), Royal Prince Alfred Hospital (NSW), Westmead Hospital (NSW), Gold Coast University Hospital (QLD), Joan Kirner Women's and Children's Hospital (VIC), Nepean Hospital (NSW), Wellington Hospital (New Zealand), Auckland City Hospital (New Zealand), Southmead Hospital (Bristol, UK), University College London Hospitals (UK) and British Columbia Children's and Women's Hospitals (Vancouver, Canada).

A sample size of 954 is required to detect a difference of at least 4 points on the cognitive sub-score at 2 years corrected postnatal age. This calculated sample size assumes 90 % power, 5 % significance level, standard deviation of 15 points, with a 2-sided t-test, 10 % loss to follow-up, and 30 % adjustment for multiple births. A blinded interim analysis will be performed after 50 % of participants have reached the 2 year endpoint to assess the assumptions in the sample size calculation.

The circadian biology/physiology sub-study (n=48/strata) has an 80 % power to detect a significant difference (at the 5 % level) in trend for the melatonin amplitude between control and intervention groups, using Wilks likelihood ratio test, assuming: 6 observations for each individual at time points 0, 1, 2, 4, 8, 12 weeks; an exponential increase in control means from 0 to 50 pg/mL and intervention means from 0 to 100 pg/mL; a standard deviation of 23.6 pg/mL;⁵⁸ a LEAR model for monotonically decreasing correlation between individual observations with a base correlation of 0.5 and a decay rate of 0.3, and; the open-source, web-based GLIMMPSE.57

Recruitment rates will be determined by the 477 infants required for the < 28 w gestation strata, who are most in demand for enrolment in neonatal clinical trials. Recruitment of an average of 18 infants/month in the < 28 w strata is achievable across 9-10 neonatal units (average 2 infants/month/site) to achieve our full study enrolment by 30 months after obtaining full study funding. The participation of up to an additional 10 study sites will be sought as necessary to ensure full study recruitment targets are achieved.

6.2 **Participant Inclusion Criteria**

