10.1 Statistics and Interim Analysis

Data will be analysed in R software (open-source) on an intention to treat basis by the trial biostatistician ([name]) and performed blinded to study group assignment.

Missing data will be handled via multiple imputation.

Children unable to be tested on Bayley-4 due to death, disability, severe delay or performance below threshold for individual composite scores will be assigned a score of 49.

Comparability of study groups at baseline will be based on patient demographic data (birth weight Z-score, gestation, exposure to chorioamnionitis and maternal steroids, maternal shift work) and baseline physiological circadian rhythmicity determined at randomisation.

Descriptive statistics will include mean (SD), median (IQR) for continuous variables with symmetric and asymmetric distributions, respectively, and counts/percentages for categorical variables.

Cognitive scores between the two groups at 2 years cPNA (primary outcome) will be analysed using (1°) ttest and (2°) linear mixed effects regression, adjusted for socioeconomic status, parental risk index, sex, birthweight Z score, gestation age, antenatal and postnatal steroid use, key neonatal morbidity count and including random effects for multiple birth ID and site. The false discovery rate employed for all secondary analyses will use the Benjamini-Hochberg algorithm.

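### Dividing by 0.7 for multiple births is not a design effect, so 954 infants and 90 % power do not describe a trial that allocates siblings together and analyses all of them

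*Protocol*

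**What the plan says.** Section 10.2 sets out the calculation in steps. The base is "A 2 sample t-test for mean difference of 4 points with SD of 15 points = 297 subjects/group", at 90 % power and two-sided 5 % significance, "for a known population standard deviation of 15 points". The total of 594 is rounded up to 600, then inflated for multiple births and loss: "600/0.7/0.9 = 952.3 subjects". This is rounded to 954. Sections 2.1 and 6.1 repeat the 954 and the 30 % adjustment.

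Section 5.3 fixes how siblings are allocated: "Infants from multiple pregnancies will be assigned to the same group". Section 10.4 evaluates all recruited infants except those withdrawn before discharge or whose parents object; it does not drop multiples. Section 10.1 lists a t-test first for the primary outcome and second a linear mixed model "including random effects for multiple birth ID and site". It also assigns a score of 49 to children who cannot be tested because of death, disability or severe delay.

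On re-checking, section 6.1 says: "A blinded interim analysis will be performed after 50 % of participants have reached the 2 year endpoint to assess the assumptions in the sample size". Section 10.2 places such checks at 25 % and 50 %. Sections 5.7 and 9.2.1 allow the sample size to be adapted as data accumulate. None of these sections gives an ICC, a cluster size or a recalculation formula.

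**The concern.** Dividing by 0.9 is right for loss to follow-up, because a lost infant supplies no outcome. Dividing by 0.7 applies the same logic to infants of multiple births, who do supply outcomes. What co-allocation of siblings costs is some precision: the second twin adds less than an independent infant would, by an amount that depends on how alike siblings' scores are. That loss is measured by a design effect, which needs the share of infants from multiples, the set size and the ICC. The protocol gives the first ambiguously and the other two not at all.

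Two things are at stake. The size and power quoted in sections 2.1, 6.1 and 10.2 are not those of the design described. And the interim check is meant to assess the assumptions of this calculation, yet the calculation contains no sibling correlation to assess and does not show how much margin exists if the SD proves larger than 15.

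**Working it through.** **Inputs from the protocol:** difference 4, SD 15, two-sided alpha 0.05, power 90 %, 10 % loss, 30 % multiples (10.2); equal groups and siblings allocated together (5.3). **Assumptions of this check:** all multiples are twins (m = 2); ICC 0.05, 0.5 and 0.9, with 1 as the limit.

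**1. The plan's own figure.** The noncentral t distribution gives 90.05 % power at 297 per group, total 594. Then 600/0.7/0.9 = 952.4, stated as 954. The arithmetic reproduces; the question is the method.

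**2. What the stated 90 % implies.** 954 × 0.9 = 858.6 infants analysed. 954 × 0.9 × 0.7 = 601, and 601 independent infants give 90.4 % power. The stated power is thus what results if the 30 % contribute nothing. The inflation factor is 1/0.7 = 1.43.

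**3. Design effect.** For an unweighted infant-level comparison with f = share of infants from multiples:

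DE = 1 + f(m − 1) × ICC; effective N = 858.6/DE; N for 90 % = 594 × DE/0.9.

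*Reading A: 30 % of infants are twins (f = 0.30)*

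| ICC | DE | Effective N | Power at 954 | N for 90 % |
|---|---|---|---|---|
| 0.05 | 1.015 | 846 | 97.2 % | 670 |
| 0.5 | 1.150 | 747 | 95.3 % | 759 |
| 0.9 | 1.270 | 676 | 93.3 % | 838 |
| 1 | 1.300 | 660 | 92.8 % | 858 |

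*Reading B: 30 % of pregnancies are twin (f = 0.6/1.3 = 0.46)*

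| ICC | DE | Effective N | Power at 954 | N for 90 % |
|---|---|---|---|---|
| 0.05 | 1.023 | 839 | 97.1 % | 675 |
| 0.5 | 1.231 | 698 | 94.0 % | 812 |
| 0.9 | 1.415 | 607 | 90.6 % | 934 |
| 1 | 1.462 | 587 | 89.7 % | 965 |

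A factor of 1.43 needs an ICC of (1.43 − 1)/0.30 = 1.43 under A, which cannot occur, and (1.43 − 1)/0.46 = 0.93 under B, which is high but possible.

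**4. Power for the mixed model.** A model that weights sets optimally has DE = 1/[(1 − f) + f/(1 + (m − 1) × ICC)]. Under A at ICC 0.9 this is 1.17 rather than 1.27, and power is 95.1 % rather than 93.3 %. The two formulas belong to different analyses.

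**5. The t-test listed first.** A t-test that ignores the pairing uses a standard error too small by √DE. Its true two-sided type I error is 2 × [1 − Φ(1.96/√DE)]: under A, 6.8 % at ICC 0.5 and 8.2 % at ICC 0.9.

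**6. Sensitivity to the SD.** Assume tested children have SD 15 and mean M, and a proportion p is scored 49. Then variance = (1 − p) × 225 + p(1 − p)(M − 49)². With p = 3 % and M = 95 the SD is 16.7; with p = 5 % and M = 100 it is 18.4. Power at 954 (reading A, ICC 0.5, unweighted) is then about 90 % and 84 %. The values of p and M are assumptions; the protocol gives neither.

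**The case against.** The strongest reply is that nothing operational is wrong: the steps are transparent and reproduce, the inflation errs on the safe side, and the recommended N is unchanged. That stands, and it limits the point to a misdescribed basis.

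Four stronger readings are tempting and are not supported:

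- *The trial is underpowered.* On the plan's own SD, power at 954 exceeds 90 % in every case shown except reading B at ICC 1, where it is 89.7 %. The lower figures in step 6 come from an assumed larger SD, not from the multiple-birth factor.
- *The implied ICC is impossible.* This holds only if 30 % means infants. If it means pregnancies, 1.43 matches an ICC of about 0.93 and power is close to the stated value. The protocol does not settle which is meant.
- *The interim check will reuse division by one minus the multiple share.* No section gives a recalculation rule; the method may sit in an analysis plan or committee charter not at hand. What can be said is that the calculation to be checked contains no ICC.
- *The MRI sub-study is misstated as having 90 % power.* Section 5.1.7 mentions "adjusting for missing subjects (10 %) and 30 % multiple births" but states no power and shows no division by 0.7, and section 10.2 gives 80 % as the general target for sub-studies.

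It is also fair to object that replacing 90 % with a single 95 % would create a new misstatement, because the score of 49 may widen the SD and because the design effect must match the analysis quoted. Both points are taken into the fix.

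**Conclusion.** The point holds as a defect in the stated basis of the sample size. Division by 0.7 is a drop-out adjustment applied to infants who stay in the analysis. It corresponds to no stated ICC, and under one reading of the 30 % to no attainable one. With a proper design effect, the N needed for 90 % power at ICC 0.05 to 0.9 is about 670 to 838 (30 % of infants) or 675 to 934 (30 % of pregnancies), and 954 gives 91 % to 97 % across both. These figures rest on the plan's 4 points, SD 15 and 10 % loss, on twins only, and on assumed ICCs. The error is conservative. It still deserves correction because 954 is presented as required for 90 % power, because the interim check is directed at these assumptions, and because the analysis listed first ignores the clustering that the sizing tries to allow for.

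**What to change.** Keep N = 954. In section 10.2, with matching wording in 2.1 and 6.1:

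1. Say whether the 30 % is of infants or of pregnancies, and state the assumed set size.
2. Replace the division by 0.7 with 1 + f(m − 1) × ICC if the power quoted is for an unweighted infant-level comparison with cluster-robust error, or with 1/[(1 − f) + f/(1 + (m − 1) × ICC)] if it is for the mixed model. State the assumed ICC and a range.
3. Restate the power at 954 for the analysis it belongs to, and make that analysis one that accounts for sibling clustering, which the t-test listed first in 10.1 does not.
4. Give that power over a range of SDs above 15, because of the score of 49, rather than as a single figure.
5. State that the blinded interim check re-estimates the SD, the share of infants from multiples and the within-set correlation, and enters them in this formula.

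Recruitment and trial procedures do not change. The cost is wording, an ICC assumption that has to be stated and defended, and a change to the primary test so that it respects the clustering.

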5.1.2.2 Long-term (2 y cPNA) secondary outcomes

- Survival
- Proportion of scores < 1 SD and < 2 SD below mean, for the primary cognitive sub-score outcome at 2 y cPNA
- Individual components of the Bayley-4 at approximately 2 y cPNA
- Neurobehaviour using the Infant Toddler Social-Emotional Assessment (ITSEA)⁵³
- Social communication using the Communication and Symbolic Behaviour Scales Infant-Toddler Checklist (CSBS-ITC) for early recognition of risk behaviours that may be predictive of later behavioural difficulties such as diagnosis of autism spectrum disorder
- Growth velocity
- Anthropometry including weight, height, BMI, fat-free mass
- Primary caregiver mental well-being
 - GAD-7
 - Center for Epidemiologic Studies Depression Scale Revised (CESD-R).
- 5.1.3 Circadian rhythm biological sub-study (KEMH only, n=~70): confirming intervention effect on rhythms
 - Time to onset, mesor, amplitude, and acrophase of circadian rhythms in temperature, heart rate, oxygen saturation, salivary melatonin and cortisol and/or urinary melatonin, and buccal cell clock gene expression at study entry, 7 d, 14 d, 28 d and then 4 weekly until discharge home.
- 5.1.4 Social Communication sub-study (n=infants identified at risk of ASD using the CSBS-ITC, in centres where ADOS-2 testing is available)
 - Assessment at 2 years corrected postnatal age with The Toddler Module of the Autism Diagnostic Observation Schedule - Second Edition (ADOS-2)⁵⁴. Two outcomes will be reported from the ADOS-2.
 - the continuous scores of the ADOS-2 (i.e., autism behavioural severity)
 - the dichotomous outcome of whether or not children exceed the 'ASD' threshold (to be defined).
- 5.1.5 Neonatal lung function and body composition sub-study (KEMH only, n=128)
 - Tidal volume
 - Respiratory rate
 - Area under the flow volume curve
 - Body volume
 - Body fat and fat free mass, and % body fat

5.1.6 Measurement of infant sleep quality and duration sub-study

- Parents will be asked to complete the Brief Infant Sleep Questionnaire (BISQ-R; 33 items) at 2 months and 6 months corrected postnatal age, to provide detail on their infants sleep behaviours over the previous 2 weeks.
- Parents will also be asked to keep a sleep diary of their own sleep behaviours over the same interval.

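### The blanket rule for sub-study sizes in section 10.2 does not describe the circadian or MRI sizing, the circadian size is given in two ways that do not reconcile, and the lung function size carries no allowance for multiples.

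*Protocol*

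**What the plan says.** Protocol section 10.2 sets one rule for every sub-study: "Sample sizes for sub-studies target 80 % power to detect 0.5 SD mean difference with significance at the 5 % level". The same section sizes the main trial differently: "This calculated sample size assumes 90 % power, 5 % significance level", "with a 2-sided t-test, 10 % loss to follow-up, and 30 % adjustment for multiple births". It applies the last two items by dividing by 0.7 and 0.9, and ties the 10 % to the long-term outcome.

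The sub-study sizes appear elsewhere in the protocol:

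- **Circadian, section 5.1.3:** "Circadian rhythm biological sub-study (KEMH only, n=~70".
- **Circadian, section 6.1:** "The circadian biology/physiology sub-study (n=48/strata) has an 80 % power to detect a significant difference". The target there is a trend in melatonin amplitude. It assumes "6 observations for each individual at time points 0, 1, 2, 4, 8, 12 weeks", an exponential rise to 50 pg/mL (control) and 100 pg/mL (intervention), an SD of 23.6 pg/mL and a LEAR correlation (base 0.5, decay 0.3). Sections 5.1.3 and 7.1.7 sample only until discharge home.
- **Lung function and body composition, section 5.1.5:** "Neonatal lung function and body composition sub-study (KEMH only, n=128". No effect size, power or inflation is given.
- **MRI, section 5.1.7:** 208 scans, 104 per group, to find "differences in the primary outcome of MRI Global Brain Abnormality Score (GBAS) of 2.85 assuming a standard deviation of 5", adjusted for 10 % missing and 30 % multiple births. No power is given.

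Section 5.3 uses two gestation strata and allocates siblings to the same arm.

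**The concern.** A reader who takes section 10.2 at its word will read each sub-study as an 80 %-powered comparison for half a standard deviation. For the circadian sub-study that is not the basis used, and the protocol does not settle how many infants will be studied. Section 7.1.7 treats this sub-study as essential to explaining mechanism, so its size and sensitivity need to be clear before the results are read. For MRI, the stated difference and the blanket rule cannot both describe 208. For lung function, the allowance that the main trial and the MRI sub-study both make for multiples is absent, so a null result could be credited with more power than it had.

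**Working it through.** All t-test figures use the noncentral t, two-sided 5 %, 1:1. Sidedness is not stated for the sub-studies; two-sided is assumed, as in the main trial.

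**Check on the main trial.** 4/15 = 0.267 SD at 90 % needs 296.5, so 297 per group, as printed. 600/0.7/0.9 = 952.4, which agrees with the protocol up to rounding. The trial's inflation rule is therefore N/0.63.

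**Circadian.**

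1. 48 per stratum x 2 strata = 96. If 48 is per arm within each stratum, the total is 192. Neither is about 70. The only route found to about 70 is 48/0.7 = 68.6, which the protocol does not state.
2. The basis is not 0.5 SD. The assumed final difference is (100 - 50)/23.6 = 2.1 SD, in a repeated-measures test.
3. To test the 80 %, I used a Hotelling group-by-time test with the section 6.1 visits, SD and LEAR values. The exponential rate is not given, so 0.05 to 0.5 per week was assumed. With 48 in a stratum (24 per arm) and all six visits, power is about 100 % at every rate. With 35 it is also above 99.9 %. If the decay is instead applied per week, the figures are 99 % or more for 48 and 95-99 % for 35. None of these is 80 %.
4. Visits: week 12 for an infant born at 28-31 w falls at 28 + 12 = 40 to 31 + 12 = 43 w PMA. For birth at 24-27 w it falls at 36-39 w PMA. Since sampling ends at discharge, many infants in the older stratum may have no week-12 visit, where the assumed separation is largest.

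**MRI.**

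1. 2.85/5 = 0.57 SD.
2. At 80 %: 49.3, so 50 per arm; 100/0.63 = 159. This is not 208.
3. At 90 %: 65.7, so 66 per arm; 132/0.63 = 210. With the normal approximation, 65 per arm gives 130/0.63 = 206. The stated 208 lies between the two.
4. In reverse: 208 x 0.63 = 131 effective infants. Power is 90 % for 2.85 points and 81 % for 0.5 x 5 = 2.5 points.

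**Lung function.**

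1. 0.5 SD at 80 % needs 63.8, so 64 per arm and 128 in total; power is 80.1 %. The stated 128 is this number with nothing added.
2. If 128 is the number recruited, power at 0.5 SD is:

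| Allowance | Effective n | Power | Detectable at 80 % |
|---|---|---|---|
| None | 128 | 80.1 % | 0.50 SD |
| Twin design effect, ICC 0.5: 1 + 0.3 x 0.5 = 1.15 | 111 | 74 % | 0.54 SD |
| Twin design effect, ICC 1: 1 + 0.3 x 1 = 1.30 | 98 | 69 % | 0.57 SD |
| Trial's multiples rule: x 0.7 | 90 | 65 % | 0.60 SD |
| Multiples rule and 10 % loss: x 0.63 | 81 | 60 % | 0.63 SD |

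The design-effect rows assume that 30 % of infants are twins with both siblings in the sub-study; the ICC values are assumptions.

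**The case against.** The strongest reply is that no sub-study is shown to miss a target set for it.

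- **Lung function.** 128 does deliver 80 % at 0.5 SD, and section 10.2 promises no inflation for sub-studies. Section 10.2 ties the 10 % loss to the long-term outcome, while tidal breathing and PeaPod are measured at about 36 weeks. Dividing by 0.7 treats every multiple as lost, which is harsher than a design effect. This largely stands: it is why a range is given and why 60 % is only its lower end. It is not complete, because fat-free mass is also measured at 2 years and the MRI sub-study applies 10 % to a term-age scan. Some allowance for siblings in one arm is still due.
- **MRI.** 208 gives 81 % at 0.5 SD even after inflation. This stands in full; only the description is wrong.
- **Circadian.** A reader might infer that going from 48 to 35 per stratum cuts the stated 80 % substantially, or that 70 infants are too few for 0.5 SD. Neither is supported. The 80 % does not reproduce, so it cannot be scaled down; under the section 6.1 inputs with all six visits, 35 per stratum loses almost nothing; and 0.5 SD is not this sub-study's target. A reader might also put a figure on the power lost when week 12 is missing. The protocol gives no discharge ages and no growth rate, and the pre-discharge window of about 34-36 w PMA in section 7.1.13 belongs to another sub-study. The question is fair, but the loss cannot be quantified.

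**Conclusion.** The point holds as a set of inconsistencies in what the protocol itself states.

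- **Circadian:** a plain contradiction, about 70 against 96 (or 192). The claimed 80 % does not follow from the stated inputs, which give about 100 % with all six visits under assumed exponential curves. The visit schedule behind it may not exist for many infants born at 28-31 w.
- **MRI:** a mislabelled but adequate size, at 90 % for 0.57 SD or 81 % for 0.5 SD.
- **Lung function:** an omission, not a contradiction. 128 meets the target only as 128 independent, analysable infants. If it is the number recruited, power is 65 % under the trial's own multiples rule, about 69-74 % under a twin design effect with ICC 1 to 0.5 (assumed), and 60 % only if the 10 % loss also applies.

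The stronger reading, that all three sizes contradict their stated power, goes too far. The correction is worth making because these figures will govern how null sub-study results are read.

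**What to change.** Restate the figures; do not enlarge the sub-studies.

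1. **Circadian (5.1.3, 6.1):** give one n, and say whether it is per stratum, per arm or in total. Recompute power, or the detectable difference, from the visits expected before discharge in each stratum, state the growth curve used, and replace the 80 % figure.
2. **MRI (5.1.7):** state either 2.85 points at 90 % power or 2.5 points at 80 %.
3. **Lung function (5.1.5):** say whether 128 is recruited or analysable. If recruited, restate the power or detectable difference with an allowance for multiples, say whether the 10 % loss applies to each measure, and name the rule used.
4. **Section 10.2:** reword the blanket sentence so that it names only the sub-studies it describes.

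The cost is text in five sections and one recalculation. Some stated figures will look less favourable. No recruitment is added.
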